6.3 Randomization

Prior to randomization it must be determined that the patient meets all entrance criteria. This includes the completion of all screening tests to determine eligibility. The randomization schedules with patients allocated to the Tixel or control LipiFlow group in a 1:1 ratio will be prepared for each site. Each envelope will have a sequential envelope number on the outside and contain the assigned treatment procedure inside. Before the treatment, the assigned personnel will open the lowest numbered envelope. The envelope number will be documented on the study source documents and in the EDC. Randomization will take place at the treatment visit prior to patient treatment. There are no criteria for crossover in this study, so all patients must be treated according to the arm to which they are randomized.

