4.2 Description of the Study

This study is a randomized, open-label, pilot clinical study comparing the Tixel device to an active control, which will be the LipiFlow System. The goal of this study is to compare between the Tixel device and the LipiFlow System and estimate the magnitude of the differences, if they exist, in terms of safety and effectiveness. A total of up to 30 patients (60 eyes) will be randomized for bilateral treatment and will be assigned in a 1:1 ratio into the Tixel treatment group or the control group at up to 2 study sites in Israel and/or Europe. The evaluator will be masked as to the randomization assignments. Both eyes will receive the same randomized assignment and both eyes of each patient will be evaluated at all time points. One eye will be selected as the designated "study eye" for statistical purposes: The study eye is the eye with the lower baseline TBUT. If both eyes have the same TBUT, the right eye will be the study eye. Outcome Measures

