7.4 Effectiveness Analyses

- Primary endpoint

The change from baseline at 4 weeks in TBUT in both study arms will be calculated along with 95% confidence interval. The Paired T-test or Signed rank test for two means (paired observations) (as is appropriate) will be applied for testing the statistical significance of the change within each study group.

Ho: $\mu h - \mu c < 1.5$

HA: $\mu h - \mu c \ge 1.5$

where μ 4w and μ base are the mean at 4 weeks and at baseline, respectively.

- Secondary effectiveness endpoints
- The change from baseline in the TBUT at 4 weeks will be analysed for non-inferiority with a margin of 1.5 using a one-sided two-sample t-test. The non-inferiority hypothesis set will be:

Ho: $\mu h - \mu c > 1.5$

HA: $\mu h - \mu c \leq 1.5$

where μ t and μ c are the mean changes from baseline for Tixel and control, respectively. Thus, the upper limit of the two one-sided 97.5% CI must be < 1.5 in order to demonstrate Tixel non-inferiority.

- The change from baseline at 12 weeks in TBUT will be calculated along with 95% confidence interval. The Paired T-test or Signed rank test for two means (paired observations) (as is appropriate) will be applied for testing the statistical significance of the changes within each study group.
- The change from baseline at 4 weeks and 12 weeks in the Ocular Surface Disease Index (OSDI) will be calculated along with 95% confidence interval. The Paired T-test or

Signed rank test for two means (paired observations) (as is appropriate) will be applied for testing the statistical significance of the changes within each study group.

• The change from baseline at 4 and 12 weeks in the MGS score will be calculated along with 95% confidence interval. The Paired T-test or Signed rank test for two means (paired observations) (as is appropriate) will be applied for testing the statistical significance of the change within each study group.

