7.7 Sample Size Justification

15 patients will be enrolled in each treatment group.

Sample size rationale:

The sample size calculation was based on an expected change from baseline at 4 weeks in TBUT score of 1.5 seconds with a standard deviation of 1.9 seconds within each study group.

Sample size justification:

A sample size of 15 will have 80% power to detect a difference in means of 1.5 assuming a standard deviation of differences of 1.9 (effect size of 0.78), using a paired t-test with a 0.05 two-sided significance level.

Reference:

7.8 **Poolability Analysis**

Patient demographic characteristics and background variables shall be summarized. To ensure poolability in case of more than one site, primary effectiveness will be analysed by site.

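### The only between-arm efficacy test uses neither site, although randomisation is by site, nor baseline TBUT; adjusting for both costs almost nothing and may sharpen the comparison

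*Combined protocol and SAP*

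**What the plan says.** Section 4.2 plans up to 30 patients, assigned 1:1, "at up to 2 study sites in Israel and/or Europe". Section 6.3 adds that the schedules are made separately by site: "in a 1:1 ratio will be prepared for each site". It gives no block size.

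The primary analysis in section 7.4 is within-arm: a paired t-test or signed rank test that "will be applied for testing the statistical significance of the change within each study group". The between-arm comparison is listed among the secondary endpoints. There the 4-week TBUT change "will be analysed for non-inferiority with a margin of 1.5 using a one-sided two-sample t-test", judged against a one-sided 97.5% limit. No covariate is named.

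Site is used only in section 7.8: "To ensure poolability in case of more than one site, primary effectiveness will be analysed by site". Because primary effectiveness is the within-arm change, that analysis neither adjusts nor checks the between-arm difference. Section 7.1 leaves further detail to a SAP that is to be final before database lock.

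**The concern.** When allocation is balanced within site, a difference between sites in mean TBUT change falls equally on both arms and largely cancels from the treatment difference. A plain two-sample t-test still counts it as residual noise. The standard error is then overstated, the interval is wider than it need be, and the test rejects less often than its nominal level allows. A similar argument applies to baseline TBUT. It is measured on every patient, and any part of the change that it predicts is left in the residual.

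The between-arm interval is what serves the aim stated in section 4.2, of comparing the two devices and estimating how far they differ. At 15 per arm it has little precision to spare.

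**Working it through.** **Inputs from the documents.** 15 per arm and SD of change 1.9 s (7.7); margin 1.5 s and one-sided 0.025 (7.4); one or two sites (4.2).

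**Assumptions.** True difference zero, equal SDs, no dropout. D is the difference between the two sites in mean TBUT change, and r is the correlation of baseline TBUT with change. The documents give neither.

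**1. The plan's own figure.** Exact noncentral-t power for a paired t-test with n = 15 and two-sided 0.05 is 81.1% at 1.5/1.9 = 0.789, and 80.2% at the stated effect size of 0.78. The 80% in 7.7 is reproduced, but it belongs to the within-arm test.

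**2. The between-arm test with no site effect.**
- Standard error: 1.9 × √(2/15) = 0.694 s.
- 95% half-width: t(0.975, 28 df) × SE = 2.048 × 0.694 = 1.42 s.
- Noncentral-t power with noncentrality 1.5/0.694 = 2.16 and 28 df: 55.1%.
- By symmetry, at a true difference of zero this holds whichever sign convention is used for the margin.
- For 80% power, about 26 per arm (normal approximation) or 27 (exact t) would be needed.

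**3. Leaving site out.** Take two sites with 8 + 8 and 7 + 7 patients. The true standard error stays at 0.694 s. The expected unadjusted residual variance becomes 1.9² + 30 × (16/30) × (14/30) × D²/28 = 3.61 + 0.267 D².
- D = 1 s: residual SD √3.877 = 1.97 s, half-width about 1.47 s.
- D = 2 s: residual SD √4.677 = 2.16 s, half-width about 1.62 s.

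Simulation of both analyses, within-site SD 1.9 s, one-sided 0.025:

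| D (s) | Power unadjusted | Power with site | One-sided error unadjusted |
|---|---|---|---|
| 0 | 55% | 55% | 2.5% |
| 1 | 52% | 55% | 2.1% |
| 1.5 | 49% | 55% | 1.8% |
| 2 | 44% | 55% | 1.4% |

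With site in the model the error stays near 2.5% throughout.

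If 1.9 s is instead the total SD, the within-site SD is √(3.61 − D²/4), which is 1.83 s at D = 1 and 1.62 s at D = 2. Power is then 55% unadjusted against 58% adjusted at D = 1, and 55% against 69% at D = 2.

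The adjusted model gives the narrower interval once D exceeds about 0.2 s. At D = 0 the lost degree of freedom moves power from 55.1% to 55.0% and the half-width from 1.421 to 1.424 s.

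**4. Leaving baseline TBUT out.** Adjusted residual SD is 1.9 × √(1 − r²), with 27 df (t = 2.052).

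| r | Residual SD (s) | Half-width (s) | Power |
|---|---|---|---|
| 0 | 1.90 | 1.42 | 55.0% |
| 0.3 | 1.81 | 1.36 | 59% |
| 0.5 | 1.65 | 1.23 | 67% |
| 0.6 | 1.52 | 1.14 | 74% |

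This gain does not need a second site.

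**5. Sensitivity to small imbalance.** With total SD 1.9 s and an 8/7 and 7/8 split, the unadjusted difference shifts by D × (8/15 − 7/15) = D/15, in a direction set by chance.
- Shift against Tixel: unadjusted power about 51% (D = 1) and 46% (D = 2), error about 1.7% and 0.6%.
- Shift in favour of Tixel: power about 59% and 63%, error about 2.7% and 1.8%.
- With site in the model: power about 58% and 69%, error near 2.5%, in both directions.

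**The case against.** A reader might infer that, because randomisation is by site, the planned interval is necessarily too wide and power is being wasted. The documents do not support that. The trial may run at one site, where the issue disappears. With two sites, no between-site variance is given, so D is an assumption. At within-site SD 1.9 s the loss is about 3 points at D = 1 s and reaches 6 points only at D = 1.5 s, which is as large as the whole expected change in 7.7. Nor is conservatism assured: a one-patient imbalance of arms within each site can push unadjusted power and error either way at D = 1 s.

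A reader might also blame the 1.42 s half-width on the missing terms. That figure arises with no site effect at all; it comes from 15 patients per arm.

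It is fair, too, that the test is secondary in a pilot, that a conservative error does not favour a false non-inferiority claim, and that section 7.8 sets no pooling test or rule that its small by-site groups (15/2, about 7–8 per arm per site) would have to support.

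These points limit the size of the concern but do not remove it. Deferring detail to a later SAP does not replace a test that 7.4 already names. The baseline gain does not depend on a second site. Where either term turns out to be unnecessary, including it costs about 0.1 point of power.

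**Conclusion.** The concern holds in a conditional form. The plan randomises by site but compares the arms with a test that uses neither site nor baseline TBUT. A site loss requires two enrolling sites, near-balance within site (which per-site 1:1 schedules aim at but no stated block size secures) and a real difference between sites. It then ranges, at within-site SD 1.9 s, from about 3 points of power at D = 1 s to about 10 at D = 2 s; if 1.9 s is the total SD, the gain from adjustment is about 3 and 14 points. With one site or no site difference it is nil. The baseline term offers about 4 to 19 points for r between 0.3 and 0.6, and nothing if r is zero. All these sizes rest on assumed D and r.

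The missing terms are not the main weakness of this test. If the within-site SD is 1.9 s, power with site in the model is still only about 55%. The within-arm primary analysis and its sample size are unaffected. The change is still worth making because the possible gain is material and the cost is close to nothing.

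**What to change.** In section 7.4, replace the two-sample t-test with a linear model for 4-week TBUT change containing arm, baseline TBUT of the study eye and, if two sites enrol, site. Report the adjusted Tixel minus LipiFlow difference with its 95% CI, and compare that interval with the non-inferiority margin. Carry the same model into the SAP before database lock. Keep the by-site results in section 7.8 and label them descriptive.

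The cost is a change of wording and at most two degrees of freedom. All the data are already collected, and neither the sample size nor the visit schedule changes.

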6.4 Schedule for Study Visits

For the Tixel:

After the randomization to the Tixel arm, each patient will undergo 3 treatment sessions (Day 0, Week 2, Week 4) at 2 weeks intervals (+/-3 days) from the previous treatment, and follow-up sessions at 4-weeks (+/-7 days) and 12-weeks (+/-14 days) after the last treatment session.

For the LipiFlow:

After the randomization to the LipiFlow arm each patient will undergo 1 treatment session (Day 0), and follow-up sessions at 4-weeks (+/-7 days) and 12-weeks (+/- 14 days) after the treatment session.

6.5 Treatments

The study procedure in both study arms shall be performed on both eyes on the same day.

Testing must be done in the following order:

- Concomitant systemic and ophthalmic medications (before treatment 1, only if not done during screening).
- Patient's report of the daily usage (frequency and dose) of eye lubricants. Before treatment 1, only if not done during screening. If data was collected at screening, only changes will be collected.

Before treatments 2 and 3 in the Tixel arm- patient's report will be collected since the last treatment done.

Before treatment 1, only for 10 patients randomized to a sub-set of the Tixel arm: Cornea
OCT and coded images upload to EDC and/or SharePoint. OCT assessment should be
performed before any corneal testing.

The following tests may be done again before treatment #1, only if treatment is being done on a different day than baseline exam, at the discretion of the investigator (these tests will be done prior to treatments 2 and 3 for the Tixel arm):

- Slit Lamp for Anterior Segment
- Lid Margin Abnormalities
- Eyelid Margin Assessment
- 1. Eye makeup shall be removed.
- The device shall be prepared for use in accordance with the Instructions for Use (IFU)/User Manual for the device to which the patient is randomized. An IFU/User Manual is packaged with each device that will be used in the study.
- For the LipiFlow treatment- Anesthetic eye drops shall be applied as per the Testing Methodologies for CLN 0798 study (CLN_0802).
- 4. For the Tixel treatment-Anesthetic cream/gel may be applied only on the eyelids according to the investigator discretion.
- Therapy shall be delivered in accordance with the IFU/User Manual for the device to which the patient is randomized. Refer to the Testing Methodologies for CLN 0798 study (CLN_0802) for more information.
- 6. For Tixel device treatment, the following zones will be treated at the following Parameters: Small tip, 6 milliseconds pulse duration, 400μm protrusion, single pulse in the following order:
 - 5 shots nasal, medial, temporal region directly below/above lid margin next to each other (Figure 4)
 - 5 shots a little lower/higher (Figure 4)

Figure 4-Treatment Zones With Tixel

7. Representatives from the Sponsor may be present during the study visits when required.

- 8. Throughout the treatment visit, patients will be assessed for any adverse events, including for development of entropion or ectropion, floppy eyelids, and lash integrity assessment.
- 9. Following treatment, patients will be assessed for the following:
 - Discomfort and Pain from the treatment (Tixel or LP) using the questionnaires in Appendix C. These are visual analogue scale (VAS) questionnaires using a scale from 0-10 to assess eye discomfort and pain. Both questionnaires are to be self-assessed by the patient immediately following treatment.
 - Slit Lamp Evaluation of Anterior Segment Health
 - Corneal Fluorescein Staining Slit Lamp Evaluation
 - Conjunctival staining Lissamine green
 - Intraocular Pressure
 - Assessment of Adverse Events
- 10. Post Treatment instructions following Tixel treatment:
 - Post Treatment instructions sheet will be given to the patient at baseline. The patient will adhere to the instructions following each treatment.
 - Patients should be aware that post treatment erythema, edema and some discomfort of the treated areas are possible and should not be a cause for concern.
 - It is not recommended to apply moisturizing creams for 24 hours after treatments.
 - No makeup, serum, toner or moisturizer with acids or "corrective" ingredients should be applied for at least 48 hours after treatment or until crusts have disappeared. It is preferable to apply non-perfumed makeup.
 - The patient should not tan in the treated area for at least 4 weeks after treatment. If sun exposure is necessary for short periods (up to 1 hour), a high SPF (at least 50 SPF) sunscreen must be worn on the lower and upper eyelids and sunglasses and a hat worn. Crusted skin should not be exposed to sun at all.
 - Rubbing, scrubbing and scratching the skin in the treated area should be avoided. Any tiny scabs (if present) should not be peeled away.
 - Avoid any exposure to chemical substances (such as direct exposure of the skin to cleaning substances) for at least a week after treatment.
 - Avoid exposure to dust and airborne dirt for at least a week after treatment.
 - Refrain from any sport, especially swimming and/or any other activity involving sweating, for at least a week after treatment.
 - Avoid exposure to heat (sauna stay, hot showers, etc.) for at least a week after treatment.

6.6 4-Weeks Follow-Up Visit

Patients will be required to return to the site 4 weeks (+/- 7 days) after the last treatment for the following assessments:

- OSDI (administer first, self-assessed)
- Cornea OCT- (only for the same 10 patients, in the Tixel group who performed the test at baseline). Images will be coded with site number, patient screening number, visit number and left/right eye and will be uploaded to EDC and/or SharePoint. OCT assessment should be performed before any corneal testing
- Concomitant systemic and ophthalmic medications
- Patient's report of the daily usage (frequency and dose) of eye lubricants since the last treatment
- Uncorrected distance visual acuity
- Corrected distance visual acuity
- Keratometry
- Slit Lamp for Anterior Segment Health
- Lid Margin Abnormalities
- Eyelid Margin Assessment
- TBUT (must be performed by a masked rater)
- Corneal Fluorescein Staining Slit Lamp Evaluation
- Conjunctival staining Lissamine green
- Meibomian Gland Assessment and Scoring (must be performed by a masked rater)
- Intraocular Pressure
- Assessment for Adverse Events

6.7 12-Weeks Follow-Up Visit

Patients will be required to return to the site 12 weeks (+/-14 days) after the last treatment for the following assessments:

- OSDI (administer first, self-assessed)
- Concomitant systemic and ophthalmic medications
- patient's report of the daily usage (frequency and dose) of eye lubricants since the last treatment
- Uncorrected distance visual acuity

- Corrected distance visual acuity
- Keratometry
- Slit Lamp for Anterior Segment Health
- Lid Margin Abnormalities
- Eyelid Margin Assessment
- TBUT (must be performed by a masked rater)
- Corneal Fluorescein Staining Slit Lamp Evaluation
- Conjunctival staining Lissamine green
- Meibomian Gland Assessment and Scoring (must be performed by a masked rater)
- Intraocular Pressure
- Assessment for Adverse Events

7 STATISTICAL CONSIDERATIONS

7.1 General Considerations

Descriptive statistics will be used to summarize continuous variables (number of eyes/patients [N], mean, standard deviation (SD) or standard error of the mean, median, maximum, and minimum) and categorical variables (frequency and percentage) at each assessment timepoint. Statistical comparisons within each group will be performed using appropriate statistical methods or models, and the results such as 95% confidence intervals and p values will be reported. All summary tables will be supported with individual patient and eye data listings. Baseline is defined as the last non-missing observation prior to initiation of study intervention. Analyses will be carried out using SAS software or equivalent statistical software.

Further details will be described in the statistical analysis plan, which will be finalized prior to the study database lock.

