7.5 Handling of Missing data

Every effort will be made to complete follow-up for all patients and avoid missing data, in particular regarding the primary endpoint variable. However, in the event data is missing, multiple imputation will be used. Missing data in MGS score at 4 weeks will be imputed sequentially using multiple imputation (MI) technique. The imputation model will include age, gender and MGS score at earlier timepoints.

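### The SAP may be finalised any time before database lock in an open-label trial, which leaves the primary test, its null and the TBUT imputation model open after 4-week TBUT becomes accessible

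*Combined protocol and SAP*

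**What the plan says.** **Timing of the SAP.** Section 7.1: "Further details will be described in the statistical analysis plan, which will be finalized prior to the study database lock". No earlier milestone is set, such as first randomisation or first access to outcome data.

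**Masking.** Section 4.2: "This study is a randomized, open-label, pilot clinical study comparing the Tixel device to an active control". The same section adds: "The evaluator will be masked as to the randomization assignments". Sections 4.2.1 and 4.2.2 require masked raters for TBUT and MGS. No section masks the sponsor, data managers or statistician, or restricts their access to outcomes before the SAP is final.

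**Primary test.** Section 7.4: "The Paired T-test or Signed rank test for two means (paired observations) (as is appropriate) will be applied" to the 4-week change in TBUT within each group. No rule says when each test is appropriate.

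**Primary null.** The same paragraph describes a test of whether the change within a group is significant, but then prints "Ho: $\mu h - \mu c < 1.5" as the null. The symbols there do not match the definitions beneath them, which refer to the 4-week and baseline means. Section 1.3 also calls 1.5 s a success criterion.

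**Missing data.** Section 7.5: "in the event data is missing, multiple imputation will be used". The imputation model that follows is for MGS. None is given for TBUT, the primary endpoint.

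**The concern.** Finalising the SAP just before lock is safe when nobody who writes it can connect outcomes to treatment until then. That condition is not secured here. Masked raters protect the measurement of TBUT. They do not protect the choice of how to analyse it.

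The matters still open are not minor. They decide which test is primary, what value it tests against, and how missing primary outcomes are filled in. If these are settled with 4-week results in reach, the nominal error rate no longer describes the procedure, and a reader of the report cannot tell whether the choice was made blind. With 15 patients per group, a borderline result can turn on such a choice.

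**Working it through.** **1. Can arm and outcome be known before lock?**

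- Section 6.4 gives Tixel patients three treatment sessions and LipiFlow patients one. Section 6.1.2 has case report forms for each treatment visit, so the pattern of forms identifies the arm.
- Sections 6.2 and 6.5 have corneal OCT images uploaded only for a subset of Tixel patients.
- Section 6.3: "The envelope number will be documented on the study source documents and in the EDC". This is the number and not the stated allocation, but no access limit is given.
- The primary outcome is due 4 weeks (±7 days) after last treatment and the final visit 12 weeks (±14 days) after it. The nominal gap is 12 − 4 = 8 weeks. With the windows it runs from (84 − 14) − (28 + 7) = 35 days to (84 + 14) − (28 − 7) = 77 days. Each patient's primary result therefore exists 5 to 11 weeks before that patient's last visit, and longer before lock for early enrolees.

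**2. The plan's own power figure (section 7.7).** Inputs: n = 15, mean change 1.5 s, SD of differences 1.9 s, two-sided 0.05, paired t-test.

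- Effect size = 1.5/1.9 = 0.789 (printed as 0.78).
- Noncentrality = 0.789 × √15 = 3.06, with 14 degrees of freedom.
- Power from the noncentral t distribution = 81.1% (80.2% with 0.78). The stated 80% is reproduced. This is a test against **zero**.

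**3. Effect of leaving the test open.** 300,000 simulated samples of n = 15, comparing the paired t-test with the exact signed-rank test (reject at W ≤ 25, attained level 4.8%), each two-sided at 0.05:

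| Distribution of changes | t alone | Signed rank alone | Whichever is significant |
|---|---|---|---|
| Normal | 4.9% | 4.7% | 5.6% |
| t with 3 df | 4.2% | 4.7% | 5.5% |
| Laplace | 4.5% | 4.8% | 5.7% |

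With normal changes the excess over nominal is 5.6 − 5.0 = 0.6 points. Under the planned effect, power is 81.1% (t), 78.9% (signed rank) and 82.3% (either).

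**4. Effect of leaving the null open.** Take the true mean change as the planned 1.5 s.

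- Test against zero: success probability 81.1%, as in step 2.
- Test against 1.5 s: the truth lies on the boundary of the null, so noncentrality = (1.5 − 1.5)/1.9 × √15 = 0. Success probability equals alpha: 2.5% at one-sided 0.025 or 5% at one-sided 0.05. No sample size changes this.

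**5. Imputation.** Section 7.5 names age, gender and earlier MGS as predictors of 4-week MGS. It gives no counterpart for TBUT. The documents state no dropout rate, so the size of this gap cannot be computed.

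**The case against.** The strongest reply is that much is already fixed: the primary endpoint and its time point (4.2.1), the ITT set (7.2), the study eye (4.2), a paired t-test at two-sided 0.05 for sample size (7.7), and no interim analysis (7.6). Section 7.1 sets a latest date for the SAP and not its actual date. A t-test with a signed-rank fallback is a common convention, and if a normality pre-test decided between them the simulated error rate would be 5.0%. The 5.6% assumes the more favourable test is always taken. This is also a pilot meant to estimate differences. All of that stands, and it lowers the stakes. It does not settle the null or the TBUT imputation model, and the absence of a planned interim analysis rules out a formal look but not access to data.

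Several stronger readings are tempting but not supported:

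- **That someone will see results by arm before fixing the analysis.** Section 6.5 says "Representatives from the Sponsor may be present during the study visits when required", but that is in the section on treatments. It does not show that SAP authors see 4-week TBUT.
- **That the allocation itself is recorded in the EDC.** Section 6.3 places only the envelope number there. The inference to arm rests on the visit pattern.
- **That eyes or patients as the unit is another open efficacy choice.** Section 7.1 mentions both for descriptive summaries, but 4.2 designates one study eye with a tie-break, and 7.7 counts patients.
- **That skewed changes make the test choice much more costly.** Under right skew most of the excess comes from the t-test itself, and nearly all of it is false worsening, not false improvement.
- **That signed rank is invalid here.** With symmetric changes it addresses the same centre as the mean. Combining it over imputations is awkward, not impossible.

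**Conclusion.** The concern holds as a gap in what the plan permits, not as evidence of what will happen. The deadline in 7.1 does not protect the primary analysis of an open-label trial in which only the raters are masked and arm can be inferred from the record.

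The three open choices differ in weight. The test alone costs little, about 0.6 points of type I error, assuming normal changes, n = 15 and the more favourable test always taken. The null dominates: about 81% success against zero versus 2.5% to 5% against 1.5 s, assuming a true change of 1.5 s and SD of 1.9 s as in 7.7. The imputation gap cannot be sized and matters only if TBUT is missing.

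The change is worth making because it is cheap and removes a doubt that cannot be resolved afterwards.

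**What to change.** - **Section 7.1:** replace the database-lock deadline. The SAP is finalised and dated before the first patient is randomised or, if the trial has started, before anyone writing it has access to any post-treatment TBUT, pooled or by arm. Pooled data must be covered because the primary test is of change within a group, so overall changes are already informative.
- **Section 7.4:** name the paired t-test of mean change against zero, the test powered in 7.7, as the sole primary test, with signed rank as a sensitivity analysis. Correct the printed primary hypothesis and its symbols to match, and reconcile the description of 1.5 s in 1.3 with it.
- **Section 7.5:** state the imputation model for 4-week TBUT.

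The cost is SAP work done earlier and a few sentences of text. No extra patients, visits or data are needed, and the sample size of 15 per group is unchanged.
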